## 3 STUDY DESIGN

## 3.1 Overview Study Design Summery

This registry will prospectively enroll 4,000 patients who undergo FMT at 75 sites throughout North America. Information on FMT methodology employed (e.g., screening of donor and recipient, preparation, FMT delivery) will be collected from each site. The indication for FMT as well as baseline information on recipient will also be collected. Following FMT, patients will be followed at regular intervals up to 10 years post FMT. This will include follow-up information from the patient's healthcare provider at 1 month, 6 months, 1 year, and 2 years after FMT as well as direct communication with patients at least annually up to 10 years after FMT. Follow-up information collected will be designed to assess potential short-term and long-term safety and effectiveness.

Anticipating changes in therapy from current FMT to use of other gut-related microbiota products in coming years, the Registry will be constructed with the flexibility to collect methodological and follow-up clinical information for all forms of gut-related-microbiota products and for a variety of indications besides CDI and IBD.

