## 6.2 Classification of Events

#### 6.2.1 Relatedness

The site Investigator will assess the relationship of SAEs to FMT, as related or not related, based on clinical judgment and using all available information, and may include consideration of the following factors:

- Possible alternative causes of the SAE, including the disease under treatment, pre-existing
  conditions, concomitant use of other drugs, and presence of environmental or genetic
  factors.
- The temporal association between FMT exposure and onset of the SAE.
- Whether the manifestations of the SAE are consistent with known actions or theoretical toxicity of FMT.

The causal relationship between FMT and the SAE will be assessed using one of the following categories.

- 1. Not Related:
  - Temporal relationship is lacking (e.g., the event occurred before FMT); or
  - Other causative factors explain the event (e.g. pre-existing condition, other concomitant treatment);
- 2. Possibly Related:
  - Positive temporal relationship (e.g., the event occurred within a reasonable time frame following FMT); and
  - The SAE is possibly explained by FMT and/or, and there is a lack of other causal factors.
- 3. Related:
  - Positive temporal relationship (e.g., the event occurred within a reasonable time frame following FMT); and
  - The SAE is more likely explained by FMT than by other causes.

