## 8.3 Statistical Methods

The registry will be designed in a manner that will facilitate statistical analyses for the purpose of signal detection, generation of descriptive data, and the conduct of comparative effectiveness studies. There will be several major advantages of the registry design as opposed to a system of spontaneous reporting. Most importantly, a prospective cohort of patients who undergo FMT with collection of predefined outcomes will allow accurate estimation of incidence rates. In contrast, systems that rely on spontaneous reporting have incomplete numerator data and lack denominator data. The ability to calculate incidence rates greatly facilitates both descriptive epidemiology and signal detection.

As noted above, registries are used to provide precise estimates of outcomes in real-world practice and document that potential adverse events occur at less than a pre-specified incidence with a predefined level of confidence. Thus, descriptive statistics with 95% confidence intervals will be determined for the safety and effectiveness outcomes to provide precise estimates of incidences. As mentioned above, if an adverse event does not occur in the planned population of 4,000 patients, we will have 95% confidence that the adverse event occurs at a rate of less than one in a thousand patients undergoing FMT.

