# **Supplement 1. Donor/Recipient Screening and FMT Technique Data Elements (characteristics to be collected once at initiation of site)**

## A. Transplant material

- Donor Stool (full spectrum)
  - Fresh
    - Time from donation to delivery
  - Frozen
    - Time from donation to freezing
  - Source
    - Directed donor (known to recipient)
      - Related
        - o Household versus non-household
      - Unrelated
        - Household versus non-household
    - Volunteer donor
  - o Age-matched: yes, no, or unknown
  - o Gender-matched: yes, no, or unknown
- Modified human stool (filtered/processed and/or enhanced)
  - o OpenBiome
    - Batch/Lot number
  - Other stool bank
  - o Specify bank
  - o Batch/Lot number
- "Commercial" stool product
  - e.g. RBX2660, SER-109
    - Batch/Lot number
  - Other
- Cultured bacterial product derived from stool
  - e.g. RePOOPulate
- Microbial consortia not derived from stool

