## C. Recipient Screening

- Site specific exclusion criteria (check if site protocol excludes patients with any of the following)
  - Age <\_\_

  - o Age >\_\_
  - o BMI
  - Medical conditions
    - List conditions
  - o Pregnancy/lactation
  - o Recent or ongoing antibiotic use
  - Allergy
  - Malignancy
  - o Immunosuppression
  - o Other\_\_\_
- Laboratory (baseline screening of recipient)-check any which apply
  - o HIV 1 & 2
  - o Hepatitis A
  - o Hepatitis B surface Ag
  - o Hepatitis B surface Ab
  - Hepatitis B core Ab
  - o Hepatitis C Ab
  - o RPR
  - Other

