## B. Baseline Characteristics

- Donor (if known)
  - o Age
  - o Race/Ethnicity
  - o Gender
  - o Height
  - Weight
  - Donor medical conditions (check any which apply)
    - No significant medical or surgical history
    - BMI ≥30
    - Hypertension
    - Hyperlipidemia
    - Diabetes type II
    - Depression/anxiety
    - CAD
    - Cerebrovascular disease
    - Asthma
    - Other\_\_\_
- Recipient characteristics (baseline)
  - o Age
  - o Race/Ethnicity
  - Gender

- Height
- Weight
- Medical co-morbidities
  - Metabolic (hypertension, diabetes II, hyperlipidemia)
  - Autoimmune (hypothyroid, RA, SLE)
  - Asthma/Allergic-Atopic conditions
  - Cardiovascular
  - Neurological conditions (MS, Parkinson, Alzheimer's, autism)
  - Psychological (depression, anxiety, eating disorder)
  - IBS
  - IBD
  - Immunocompromised from medical condition or medication
  - Other
- Labs (glucose, cholesterol, HDL, LDL, triglycerides, ALT, alkaline phosphatase, bilirubin, albumin, BUN, creatinine)
- CDI baseline characteristics
  - Disease characteristics (pre-FMT)
    - Mild illness (recurrent)
    - Moderate (more severe but uncomplicated disease)
    - Severe
    - Severe complicated
  - Duration of *C. difficile* infection (weeks between initial diagnosis and FMT)
  - Number of CDI episodes
  - C. difficile strain
    - o Nap-1
    - Non Nap-A
    - o Unknown
  - Other treatments courses received (and number of courses of each, if known) for CDI prior to FMT
    - o Metronidazole
    - o Vancomycyin
    - o Vancomycin taper/pulse dose
    - o Fidaxomicin
    - o Nitazoxanide
    - o Rifaximin
    - o IVIG
    - o Saccharomyces. boulardii
    - o Lactobacillus GG
    - Other probiotic
    - o Other\_\_
  - Immediate Pre-FMT treatment(s)
    - Antisecretory therapy?
      - No
      - Yes
- H2 blocker
- Proton Pump inhibotor
- o Probiotics?
  - No
  - Yes

- list
- Antibiotics?
  - No
  - Yes
- Metronidazole
- Vancomycin
- Other
- o If yes, were antibiotics stopped? (yes/no)
- Number of days off antibiotics prior to FMT
- IBD Baseline characteristics
  - o Type of IBD
    - CD
    - UC
    - IBD-U
    - Pouchitis
  - Disease location/extent
    - Montreal classification for adults >18 y/o
    - Paris classification for children <18 y/o

  - IBD treatment pre-FMT
    - Antibiotics
      - IV
      - Oral
    - Probiotics
    - Diet
      - Type of diet
    - Mesalamine
      - Oral
      - Rectal
    - Thiopurines
    - Methotrexate
    - Steroids
      - Oral

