## Supplement 6. FMT Long-term Adverse Outcomes (up to 2 years by physician report and 10 years by patient report)

- Characteristics
  - Height
  - Weight
- Serious Infection (HIV, viral hepatitis, prion, etc)
  - *Use of new drugs* 
    - o Describe
  - Surgeries or other Procedures
    - Describe
- Diagnosis of any new condition
  - o Autoimmune (hypothyroid, ITP, RA, SLE, MS, celiac, Type I diabetes, Sjogrens)
  - o Asthma
  - Allergy/atopy
  - Metabolic disease
    - Diabetes II
    - Obesity
  - o Psychiatric disorder
  - Neurologic disease
    - Parkinson's disease
    - Amyotrophic lateral sclerosis (ALS)
    - Autism spectrum diagnosis
  - Cardiovascular disease
    - Myocardial infarction
    - Coronary artery revascularization
    - Cerebrovascular accident
    - Hypertension
  - o Colon cancer
  - Other malignancy
  - Inflammatory bowel disease
    - Crohn's
    - Ulcerative colitis
    - IBD-U
  - o IBS
- IBS-C
- IBS-D
- IBS-M
- o Other
- Hospitalization
  - o Reason for hospitalization
  - o FMT related (related, possibly related, unrelated)
- Life-threatening illness
  - o Describe/diagnosis
  - o FMT related (related, possibly related, unrelated)
- Death
  - Cause of death
  - o FMT related (related, possibly related, unrelated)

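### HIV and viral hepatitis count as long-term outcomes, but no per-patient infection status before FMT is recorded, so the registry has no systematic way to separate prior from newly acquired infection

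*Protocol*

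**What the plan says.** **Outcome.** Supplement 6 (long-term adverse outcomes) lists "Serious Infection (HIV, viral hepatitis, prion, etc"). The line does not say that the infection must be new, and it asks for no date and no relationship to FMT. The infection item in Supplement 5 (first 30 days) does ask for the site or organism and for relatedness.

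**Recipient testing.** Supplement 1, part C, has the item "Laboratory (baseline screening of recipient)-check any which apply", followed by HIV, hepatitis A, B and C, and RPR. It names tests and has no field for results. The heading of Supplement 1 describes its contents as "characteristics to be collected once at initiation of site". Section 3.1 agrees: "Information on FMT methodology employed (e.g., screening of donor and recipient, preparation, FMT delivery) will be collected from each site".

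**Patient baseline.** Supplement 3, part B, records for each recipient "Labs (glucose, cholesterol, HDL, LDL, triglycerides, ALT, alkaline phosphatase, bilirubin, albumin, BUN, creatinine") and a list of co-morbidities. HIV and viral hepatitis are not on that list. The nearest entries are "Immunocompromised from medical condition or medication" and an open *Other*.

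**Purpose.** Section 8.3 says that "a prospective cohort of patients who undergo FMT with collection of predefined outcomes will allow accurate estimation of incidence rates".

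**The concern.** An incidence rate needs a population known, or at least reasonably presumed, to be free of the condition at entry. For HIV, hepatitis B and hepatitis C this matters in practice, because a chronic infection can be present for years before anyone tests for it. A diagnosis made after FMT is not the same as an infection acquired after FMT.

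The error can go either way. A prior infection found during follow-up may be counted as a harm of FMT. A true transmission may be put down to prior infection because no negative test is on file.

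Safety is the primary objective (section 2.1), and section 1.2 cites HIV and hepatitis C spread through blood products as the reason for caution. An analysis plan could not repair the gap later, because the baseline item would not have been collected. After year 2 the information comes from patients alone (section 5.1), so reconstructing a pre-FMT result at year 5 or 10 may not be possible.

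**Working it through.** **1. Where could a recipient's pre-FMT status be held?**

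- *Supplement 1, part C:* a checklist of tests, once per site. Even if completed for each patient, it would show which tests were run and not what they found.
- *Supplement 3, part B, laboratory results:* chemistry and lipids only. ALT may be raised in hepatitis but does not identify it.
- *Supplement 3, part B, co-morbidities:* metabolic, autoimmune, asthma or atopy, cardiovascular, neurological, psychological, IBS and IBD each have a counterpart among the new diagnoses in Supplement 6. HIV and viral hepatitis have none. A known infection might be entered as immunocompromised or as *Other*, but neither entry can record a negative test.
- *Section 6.2.1:* an SAE is classed as not related under the criterion "Temporal relationship is lacking (e.g., the event occurred before FMT); or" because other causes explain it. This covers SAEs only, rests on the investigator's judgment and supplies no baseline result.
- *Biorepository (section 5.2, Appendix A):* stool from at least 1,000 procedures. It does not replace recorded HIV or hepatitis results across 4,000 patients.

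None of these gives a systematic positive, negative or untested status for each patient.

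**2. The plan's own figure.** Sections 8.1 and 8.3 state that no events in 4,000 patients gives 95% confidence in a rate below 1 in 1,000. The exact one-sided limit is

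1 − 0.05^(1/4000) = 0.000749 = 0.0749%.

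The two-sided version is 1 − 0.025^(1/4000) = 0.0922%. Both are below 0.1%, so the statement reproduces.

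**3. Effect of a misclassified case (illustration).** The exact (Clopper-Pearson) one-sided 95% upper limit for k events in n = 4,000 is the 95th percentile of a Beta(k + 1, n − k) distribution.

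| Pre-existing cases counted as new | Upper limit |
|---|---|
| 0 | 0.0749% |
| 1 | 0.1185% |
| 2 | 0.1573% |

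One case is enough to cross 0.1%.

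**4. How likely is one case?** The documents give no prevalence, so this step rests wholly on assumption. Suppose 0.05% to 1% of recipients carry an unrecognised infection and 25% to 100% of these are found during follow-up.

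- Low end: 4,000 × 0.0005 × 0.25 = 0.5 expected cases, and the chance of at least one is 1 − (1 − 0.000125)^4000 = 39%.
- High end: 4,000 × 0.01 × 1 = 40 expected cases, and at least one is practically certain.

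These are cases open to misclassification. How many would be entered as post-FMT harms cannot be known from the documents.

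**The case against.** The supplements are not the final case report form. Section 5.1 calls them elements that may be collected, and other lines of Supplement 6, such as myocardial infarction, are just as terse and undated. The file's heading speaks of adverse outcomes, so a clinician reporting up to year 2 is unlikely to enter an infection known before FMT. General baseline categories and the SAE relatedness rule catch some known infections. Hospitalisation, life-threatening illness and death in Supplement 6 carry their own relatedness field. Much of this stands for infections that were already known. It does not help with infections unrecognised at FMT, and it never yields a documented negative. Room to add an element is not the same as having it.

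Three stronger readings are tempting and are not supported.

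- *A reader might infer that prior and acquired infection can never be told apart.* The routes above show that some known cases can be. What is missing is a systematic record.
- *A reader might infer that the plan sets a target of 1 in 1,000 for infection and would miss it.* Sections 8.1 and 8.3 use zero events as an illustration for any adverse event, set no target for infection, and also rely on incidence estimates with 95% confidence intervals.
- *A reader might multiply an assumed prevalence by 4,000 and call the result the number of false harms.* That counts carriers. Patients with a known diagnosis are the least likely to be entered wrongly.

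The position of the line outside the block of new diagnoses is weak evidence as well, since the nesting in that part of the text is visibly disturbed. The point rests on the wording of the line itself.

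**Conclusion.** The concern holds in a limited form. For HIV and viral hepatitis the protocol defines an outcome that is not restricted to new infection, and it records no per-patient baseline against which a later report could be judged new. The claim in section 8.3 of accurate incidence rates therefore lacks its baseline for these infections. The planned sample size and the stated precision figures are unaffected.

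The size is best given per case: one pre-existing infection counted as new raises the upper limit from 0.075% to 0.119%, and a rate below 1 in 1,000 could then no longer be claimed for that outcome. This assumes follow-up of all 4,000 patients and no true events. The expected number of such cases is unknown. This is a worthwhile and cheap improvement to data collection, not a flaw that invalidates the registry.

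**What to change.** 1. Add to Supplement 3, part B, a per-patient pre-FMT status for HIV, hepatitis B and hepatitis C: known positive, tested negative (with date), or not tested or unknown. Copy it from existing records and require no new testing. Hepatitis A and syphilis can be left out: hepatitis A does not fit the argument about chronic infection, and Supplement 6 does not name syphilis.
2. Reword the Supplement 6 item to *New serious infection since FMT or last report* and add the date of diagnosis.
3. Keep the full-cohort rate as the main figure, excluding only patients known positive for the infection in question. Report cases by baseline status (tested negative or unknown), and give the rate among tested-negative patients as a sensitivity analysis. Making that subset the main analysis would restrict the denominator to sites that happen to test recipients and lose precision.

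The cost is three short fields per patient, with a date where a negative test exists, and one reworded line with a date. Status stays unknown at sites that do not test recipients, so the change narrows the gap without closing it. It should be made before or early in enrolment, while the records are at hand.

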## **APPENDIX A: Biorepository Sub-Study Protocol**

Title: Fecal Microbiota Transplant National Registry Biorepository

*Principal Investigator:* [name], Professor, Departments of Pediatrics and Computer Science & Engineering, University of California San Diego

## 1. Facilities

Samples will be received and stored at the [name] Lab [name] on the University of California San Diego Medical School campus. The American Gastrointestinal Association's (AGA) administrative offices ([name], [name]) will track a deidentified list of participants in the FMT National Registry and the American Gut Project (AGP) barcodes assigned to those who consent to be part of the Biorepository.

## 2. Estimated Duration of the Study

10 years

## 3. Specific Aims

By collecting and characterizing the microbiomes of these samples, we aim to expand knowledge to help optimize practice in the transplantation of fecal microbiota or other gut-related microbiota products. Specific aims characterizing the FMT National Registry-AGP biobank partnership include assessing the short and long-term safety of FMT and other gut-related microbiota products, to characterize the effectiveness of FMT and other gut-related microbiota products, and to gather information and promote scientific investigation on the practice in North America.

## 4. Background and Significance

The gut microbiome functions in a symbiotic relationship with the human body at a level of complexity akin to an organ or tissue. Recent advancements in genome sequencing technology have been used to identify the tremendous diversity of these microorganisms, opening a new frontier for research into the role of the gut microbiome in health and disease. It is now well appreciated that intestinal microbiota constitute a microbial "organ" that is integral to overall host physiology, including pivotal roles in metabolism and immune system function. Initial investigations have demonstrated that alterations in the gut microbiome (dysbiosis) may play a role in a number of gastrointestinal and non-gastrointestinal disorders (e.g., Clostridium difficile infection (CDI), inflammatory bowel disease (IBD), irritable bowel syndrome (IBS), nonalcoholic fatty liver disease, obesity, diabetes, metabolic syndrome, cardiovascular disease, cancer, and many others).

The first clinical therapeutic application of this knowledge has been the use of fecal microbiota transplantation (FMT) to treat CDI. FMT involves administration of fecal material (containing intestinal microbiota) from a healthy individual (donor) to treat dysbiosis and restore beneficial intestinal flora and phylogenic diversity. FMT, which transfers highly complex microbial

communities, has proven to be beneficial in the treatment of recurrent CDI in numerous case series and a recently published randomized controlled trial. Because of recent trends in the incidence and severity of CDI and the growing body of literature, including current treatment guidelines, which support FMT, the number of physicians who perform FMT in the United States is growing. There are ongoing efforts to refine the process of FMT, with stool banks to supply carefully screened donor material and commercially available encapsulated formulations. Furthermore, investigations of FMT for the treatment of other conditions, such as IBD, are underway.

A biorepository will facilitate analysis of stool specimens and linkage of these analyses to clinical data from the FMT National Registry, thereby allowing assessment of the association of clinical effectiveness and safety outcomes with the biological characteristics of stool specimens or other gut microbiota-based products.

## 5. Research Design and Method

This biorepository will prospectively enroll at least 1,000 patients who undergo fecal microbiota transplantation (FMT) at 75 sites throughout North America and their corresponding stool donors. All of these participants will first be enrolled in the FMT National Registry, administered by the AGA. Upon consenting to enroll in the registry, individuals will be given the opportunity to also enroll in this biorepository sub-study, after explanation of the biorepository and providing an additional signature on the registry informed consent. If individuals enroll in the biorepository, they will be provided an AGP sampling kit. The AGP barcode will be linked to the participant's FMT registry code (which contains no personal health identifiers). The stool samples will be mailed to the [name] Lab [name] on the University of California San Diego Medical School campus.

For patients enrolled in the biorepository sub-study, stool samples will be collected from the recipients before FMT and at 1 month after FMT. For stool donors enrolled in the biobank, samples will be collected from the stool they have donated for FMT procedures. The [name] lab at University of California San Diego will perform microbiome data analysis in accordance with the methods of the American Gut Project which may include amplicon sequencing, metagenomics, metabolomics, and proteomics. The clinical data obtained as part of the FMT National Registry can then be linked to the analysis performed on stool specimens for investigations related to the aims outlined above for the FMT National Registry. The [name] lab will also house the biobank in BRF2 on the University of California San Diego Medical School campus.

## 6. Human Subjects

Participation in the Biorepository will be limited to individuals in the FMT National Registry; therefore, the same restrictions on participation apply as in the FMT National Registry Protocol.

## 7. Recruitment and Procedures Preparatory to Research

At the time of consenting to participate in the FMT National Registry, individuals will be given the opportunity to also enroll in the biorepository, after explanation of the biorepository and providing written informed consent. Participation is entirely voluntary.

